#### **4. Objectives**

1a: To identify the demographic and behavioural risk factors associated with incident HIV infection (based on “NAT yield” or LAg Avidity testing) among blood donors in South Africa.

Hypotheses: 1) The risk factors for incident HIV in blood donors in South Africa will include a recent change in sexual partner, older male/younger female sexual partnership, a greater number of recent sexual partners, unprotected receptive anal intercourse, and lower socioeconomic status.

1b: To identify the demographic and behavioural risk factors associated with incident HBV infection among blood donors in South Africa identified as “NAT-yields” or concordant serology and NAT positive and anti-HBc negative.

Hypotheses: 1) The risk factors for incident HBV in blood donors in South Africa will include greater number of recent sexual partners, recent scarification/tattoo/body markings, and history of personal contact with an HBV-infected person.

2a: To determine HIV subtype and drug resistance profiles among HIV positive donors with recently acquired infection based on year of donation and site of collection, and examine findings with donor demographics and risk behaviors derived in Objective 1.

Hypotheses: 1) The proportion of donors identified with incident HIV infection containing drug resistance mutations will be positively related to the proportion of HIV-positive individuals receiving anti-retroviral therapy at a population-level in South Africa

2b: To determine HBV genotype profiles among HBV positive donors with recently acquired infection based on year of donation and site of collection, and correlate findings with donor demographics and risk behaviors derived in Objective 1

Hypotheses: 1) Incident HBV infections will show differences in genotypes with genotype E increasing when compared to public health data on prevalent infections.

3: To prospectively characterize the virology, immunology and natural history of incident HIV infection among a cohort of recently infected blood donors and a small group of elite controllers in South Africa.

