### **4.3 Stratification or Randomization**

The study sample will include HIV and HBV cases who are recruited from among those with identified incident infection who return to SANBS for their results (anticipated to be ~50% of donors with incident infections). The study sample controls will be selected to achieve stratum-matching to HIV-cases by geographic region, age (5-year intervals), and population group from among donors who test negative for all infections (HIV, HBV, HCV, and syphilis) at randomly selected clinics.

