### **4.8.1 Sample size and power**

Sample size and power calculations for this study cannot be based on the assumption of independent donor sample selection. We will be selecting blood donation clinics that are similar to those clinics where the study cases were donated, and, then, from the selected clinics selecting controls. Consequently, the sampling and analytic approaches account for clustering at the clinic level. Computer simulations (Monte Carlo simulation) of the study population were run to determine the odds ratios we can detect based the assumptions of the exposure prevalence in the donor populations and the expected number HIV and HBV cases that we will be able to enroll in the study during a 3-year period. There were several factors examined in the Monte Carlo simulation, i.e., the expected number of cases, the expected number of controls per case, the correlation between proportion exposed for the cases and controls, the proportion exposed in the control group, and the difference in proportions between the controls and cases. Thus cross-classification of all of these factors created multiple experimental groups and 1,000 Monte Carlo simulations were run for each group. Calculations are based on alpha equal to 0.05, power equal to 0.8, and a two-sided test.

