### **HIV Power Calculations**

For HIV we focused on multiple sexual partners (more than one partner at the same time, or at least two partners in the previous year) as a primary risk factor in South Africa, and estimated that the prevalence of multiple sexual partners in the control and case populations. We assumed a 10% difference in the prevalence of multiple sexual partners between cases and controls. Depending on the prevalence of multiple sexual partners in the control population the odds ratio that we will be able to detect with 80% or higher power is between 1.65 and 1.94 for

a study with 300 cases and 900 controls (Table 8). In the Monte Carlo, simulation estimates for odds ratios were similar regardless of the ratio of cases to controls, 1:1, 1:2, or 1:3. That is, a 1:1 ratio would allow for similar odds ratios to be detected. This analysis assumes that the selection of controls from the same geographic regions as cases will be consistent with the assumptions of inter cluster correlations that were defined for the Monte Carlo simulation power analysis. However, there is substantial uncertainty around how similar the behavioural exposures of cases and controls between different clusters (clinics) will be. For this reason we believe including a larger number of controls per case may be required in order for the team to ensure the study meets its primary objectives. Recall that we will be accepting virtually all cases so the only way to enlarge the sample is to include more controls. Also, including more controls will allow for secondary analyses of behavioural prevalence in donors without infection. For example, the study is interested in understanding the range of relatively common to less common risk factors for newly acquired infections in blood donors in South Africa. We want to be able to detect and report findings across a range of behavioural exposures. It is not expected the distribution of all behaviors will conform to the assumptions made for the Monte Carlo power analysis. Risks other than multiple sexual partners will have different prevalence in the donor population and may have smaller differences in exposure prevalence between cases and controls within each clinic. For these reason we are planning to enroll cases and controls in a ratio of 1:3.

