The purpose of objective 1a is to identify the demographic and behavioural risk factors associated with incident HIV infection among blood donors in South Africa previously identified as “NAT-yield” and other recently acquired infection based on LAg Avidity testing as compared to controls. The outcome variable is whether or not a blood donor has HIV infection. That is, a binomial variable. The predictor variables believed to be associated with HIV in blood donors will include recent change in sexual partner, older male/younger female sexual partnership, a greater number of recent sexual partners, unprotected receptive anal intercourse, and lower socioeconomic status. Other possible predictor variables, e.g., behavioural variables, will be examined to understand their relationship to whether or not the blood donor has HIV infection. The association between the outcome variable and a predictor variable will be examined using categorical data analysis techniques. Bivariate analysis will be conducted using Chi-square tests. Analyses that include more than one predictor variable will be conducted using multiple logistic regression, which may include interaction terms. In addition, nonparametric modeling will be used when there are multiple predictor variables.

The purpose of objective 1b is to identify the demographic and behavioural risk factors associated with incident HBV infection among blood donors in South Africa previously identified as “NAT-yields” and which are anti-HBc negative. The outcome variable is whether or not blood donor has HBV infection. That is, a binomial variable. The predictor variables believed to be associated with HIV in blood donors will include greater number of recent sexual partners, recent scarification/tattoo/body markings, and history of personal contact with an HBV-infected

person. Other possible predictor variables, e.g., demographic variables, will be examined to understand their relationship to whether or not the blood donor has HBV infection. The association between the outcome variable and predictor variable will be examined using categorical data analysis techniques. Bivariate analysis will be conducted using Chi-square tests. Analyses that include more than one predictor variable will be conducted using multiple logistic regression, which may include interaction terms. In addition, nonparametric modeling will be used when there are multiple predictor variables.

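### Section 4.9 does not carry out the clinic-clustering commitment of section 4.8.1 and does not require the Objective 1 analyses to condition on the matching factors

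*Protocol*

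**What the plan says.** Section 4.8.1 states that "Sample size and power calculations for this study cannot be based on the assumption of independent donor sample selection". It goes on: "Consequently, the sampling and analytic approaches account for clustering at the clinic level". The subsection on HIV power adds that "there is substantial uncertainty around how similar the behavioural exposures of cases and controls between different clusters (clinics) will be". No intra-clinic correlation or number of donors per clinic is given.

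The synopsis calls the design frequency matched (a stratified sample). Section 4.3 describes control selection as "stratum-matching to HIV-cases by geographic region, age (5-year intervals), and population group". The HBV comparison reuses controls recruited for the HIV cases; section 4.2.2 on control recruitment foresees a subset of them, matched on the same factors at about 1:3.

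Section 4.9 gives the analysis for Objectives 1a and 1b. "Bivariate analysis will be conducted using Chi-square tests"; where there is more than one predictor, multiple logistic regression is used, possibly with interactions, together with nonparametric modelling. No clinic term, robust variance, stratification or obligatory matching covariate is mentioned. The only provision for clustering in 4.9 is under Objective 3, for repeated measurements on the same donor. The weights mentioned at the start of 4.9 are for missing data.

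**The concern.** The protocol claims a property for its analysis in one section and, in the section that specifies the analysis, names methods that lack that property as written. A reader who follows 4.9 literally would treat donors as independent and would compare cases and controls without regard to the strata used to select them.

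Frequency matching makes the controls resemble the cases on region, age and population group. If those factors also predict the exposure, the crude odds ratio is no longer the within-stratum odds ratio and lies closer to 1. The protocol gives reason to expect this: in section 4.10, under women and minorities, it says that socioeconomic and behavioural factors differ significantly between the White and Black populations.

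For HBV the controls were chosen to resemble a different case group. An unadjusted comparison can then carry ordinary confounding, whose direction depends on which group has the higher exposure.

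The first objective is "To identify the demographic and behavioural risk factors associated with incident HIV infection". The demographic part of that aim needs a statement about which demographic factors the sampling leaves estimable.

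**Working it through.** **The plan's own figures.** Inputs are from section 4.8.1 and Tables 8 and 9: "Calculations are based on alpha equal to 0.05, power equal to 0.8, and a two-sided test". With OR = [p1/(1−p1)]/[p0/(1−p0)], the three HIV rows (0.15/0.25, 0.20/0.30, 0.25/0.35) give 1.889, 1.714 and 1.615. The stated values are 1.94, 1.74 and 1.65, which are 1.5% to 2.7% higher. Power for 300 cases and 900 controls under independence is 0.966, 0.937 and 0.910, consistent with the claim of 80% or higher. The clustered simulation cannot be rerun, because its correlation and cluster sizes are not given. These figures are not disputed.

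**Matching left out, HIV.** Table 3 gives 251 Black, 29 White and 18 other donors (6 Asian, 12 Coloured), 298 with a known group. The shares are 0.842, 0.097 and 0.060. Exposure in controls is assumed at 50%, 10% and 30%; the within-group OR is 1.9.
- Controls: 0.842×0.50 + 0.097×0.10 + 0.060×0.30 = 0.449.
- Case exposure by group, p×1.9/(1−p+p×1.9): 0.655, 0.174, 0.449. Weighted: 0.596.
- Crude OR = (0.596/0.404)/(0.449/0.551) = 1.81.

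With assumed exposure of 30/10/20% the result is 1.87, and with 25/15/20% it is 1.89. This uses race only. A separate check used the Table 3 age and population shares, 20% baseline exposure and a within-stratum OR of 1.94. The average crude OR was 1.93, 1.89, 1.78 or 1.66 when the between-stratum SD of the log-odds of exposure was 0.25, 0.5, 1.0 or 1.5.

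**HIV-matched controls used for HBV without adjustment.** Among Black and White donors only, the Black share is 251/280 = 0.896 (HIV) and 161/224 = 0.719 (HBV). Suppose there is no true effect and the controls keep the HIV mix.
- Assumed exposure 0.55 in Black and 0.30 in White donors: controls 0.524, HBV cases 0.480; crude OR = 0.922/1.101 = 0.84.
- The two exposures exchanged: controls 0.326, HBV cases 0.370; crude OR = 0.588/0.483 = 1.22.

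So the bias can go either way. With the same control mix, the apparent HBV odds ratio for Black versus White is (161/63)/(251/29) = 0.30, which comes from control selection alone.

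**Can the HBV subset be matched at 1:3?** If 900 controls follow the HIV mix, about 0.097×900 = 87 are White. If 150 HBV cases follow the HBV mix, about 0.254×150 = 38 are White. That is 2.3 per case, short of 3.

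**Clustering left out.** An unadjusted test at nominal 0.05 was simulated under no effect (20% exposure, 300 cases, 900 controls, 8,000 runs per setting). Latent intra-clinic correlations of 0.03, 0.07 and 0.16 were assumed.
- Cases and controls from different clinics, 5 to 30 controls per clinic: type I error 0.054–0.065, 0.054–0.086 and 0.062–0.132 respectively.
- Cases and controls sharing clinics in a balanced 1:3 ratio: 0.037–0.051 over all settings.

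A closed form agrees for clustering in controls only. At 1:3 the controls contribute a quarter of the variance, so the inflation is 0.75 + 0.25×[1+(m−1)×ICC]. For m = 10 and ICC 0.05 this is 1.1125, giving 2[1−Φ(1.96/√1.1125)] = 0.063. For m = 20 and ICC 0.10 it is 1.475, giving 0.107.

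**The case against.** The terms chi-square test and logistic regression cover stratified and design-based versions, and covariate lists and variance estimators are often left to a statistical analysis plan, which is not shown here. Section 4.9 lets other predictors enter the model, so the matching factors are not excluded. Section 4.8.1 promises to account for clustering only; nowhere does the protocol promise to adjust for matching. All of this stands as a limit on the wording: 4.9 omits these adjustments rather than ruling them out. It does not remove the point, because the protocol itself claims an analysis that accounts for clustering and then specifies one that does not say so. A bivariate chi-square as described also cannot condition on three matching factors.

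Four stronger readings are tempting and not supported.
- A reader might infer that the odds ratios and p-values will be wrong. The documents show only that they can be biased or miscalibrated. The size depends on exposure gradients and clinic correlations that are not given, and with shared clinics the unadjusted test is near nominal or conservative.
- A reader might infer heavy attenuation for HIV. Four equal strata with exposure of 45/25/15/5% or 60/30/10/5% turn 1.9 into 1.73 or 1.61, but Table 3 puts 83.7% of HIV donors in one population group.
- A reader might set the HBV cases against the full HIV control mix. With 50/10/30% exposure a null then appears as 0.75 and a true 1.9 as 1.30. Section 4.2.2, however, plans a matched subset, and Table 9 uses 450 controls, so these figures do not describe the intended comparison.
- A reader might infer that age, race and region will be reported as unrelated to HIV. For 1a, section 4.9 does not list those three as predictors; demographic variables are named as an example only for 1b. Sex, marital status, education and employment are not matched and remain open to study.

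**Conclusion.** The point holds as an inconsistency between sections 4.8.1 and 4.9, together with an analysis that is unsuited to a frequency-matched sample unless the matching factors are included. It concerns the main comparisons of Objectives 1a and 1b.

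For HIV the likely effect is modest attenuation: about 1.8 for a true 1.9 under the stated race-only assumption, less if exposure differs little between strata and more if age and region also predict it strongly. For HBV the risk is confounding in either direction, which depends on whether the control subset is really matched; the supply of White controls suggests this may be difficult at 1:3. For clustering, p-values may be too small or too large depending on clinic overlap. All exposure gradients and correlations used here are assumptions. Table 3 covers NAT-only donors from 2006 to 2010 in all seven regions and includes some under 18, so its shares only approximate the study population.

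**What to change.** In section 4.9, for every bivariate and multivariable Objective 1 analysis:

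- Replace the unadjusted chi-square with logistic models that include region, age and population group as covariates, or with Mantel-Haenszel tests on suitably coarse strata. Crossing five zones, four population groups and 5-year age bands would give well over 100 cells for 300 HIV or 150 HBV cases, so covariates or coarse strata are preferable to full cross-classification.
- Name the treatment of clinic clustering: cluster-robust variance, GEE, a random clinic intercept or Rao-Scott tests.
- State that age, population group and region are design variables: their effects on HIV cannot be estimated from this sample, and their apparent effects on HBV reflect control selection.

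The cost is slightly wider confidence intervals and a little more analysis work. No new data are needed: the questionnaire in Appendix 7 already records the collection-site code (A3), date of birth (B2–B4) and population group (B6), and the site code maps to branch, zone and province.

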
In order to determine risk factors for incident HIV and HBV infections (Objective 1) we will conduct a frequency matched (stratified sample) case-control study with two case groups: incident HIV infected blood donors; and incident HBV infected blood donors, both to be compared to infectious marker negative controls. Cases and controls will be accrued from a geographically diverse donor pool. We will further characterize HIV clade and drug resistance profiles and determine viral loads in all cases of incident HIV infection, and HBV genotype and viral load in all incident HBV infections (Objective 2), and follow incident and elite controller HIV infections prospectively for three additional visits at 2, 3, and 6 months following index donation (Objective 3).

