**Figure 2 Approaches for HBV-positive donor testing and study entry.**

[figure not shown]

Table 1 Planned HIV testing based on index donation test results.

Index Donation Testing Result	Tests to be Conducted on Index Donation Specimens	Tests to be Conducted on Follow-up Samples	SANBS Standard Procedure Testing	REDS-III Study Protocol Testing
Serology Only Positive	Serology confirmatory (Immunocomb)	NAT	X	
	Western Blot	Serology	X	
		Western blot	X	
NAT and Serology Concordant Positive	LAg Avidity	LAg Avidity (if no index sample available)		X
	Serology confirmatory (Immunocomb)			X
	Western Blot if LAg avidity negative			X
	p24 Ag if LAg avidity negative			X
	Viral Load if LAg avidity negative			X
	Genotyping if LAg avidity negative	Genotyping (in no index sample available)		X
	Drug resistance if LAg avidity negative	Drug resistance (if no index sample available)		X
		NAT confirmatory		
		Serology confirmatory		
		Viral load		X
		Western Blot if p31 negative on previous WB		X
		p24 Ag (if p24 Ag negative on index)		X
	Rapid HIV test and counseling		X	
NAT Only Positive	NAT Confirmatory		X	
	p24 Ag		X	
	Viral Load		X	
	Genotyping	Genotyping (in no index sample available)		X
	Drug resistance	Drug resistance (if no index sample available)		X
		NAT confirmatory	X	
		Serology confirmatory	X	
		Viral load	X	
		Western Blot		X
	p24 Ag	X		

Table 2 Planned HBV testing based on index donation test results.

Index Donation Testing Result	Tests to be Conducted on Index Donation Specimens	Tests to be Conducted on Follow-up Samples	SANBS Standard Procedure Testing	REDS-III Study Protocol Testing
Serology Only Positive	Serology (confirmatory)	NAT	X	
	Anti-HBc IgM	Serology (confirmatory)	X	
	Anti-HBs	Anti-HBs	X	
	Anti-HBc Total	Anti-HBc total and IgM	X	
NAT and Serology Concordant Positive	Anti-HBc Total			X
	Viral Load if anti-HBc negative			X
	Genotyping if anti-HBc negative	Genotyping (if no index sample available)		X
		NAT confirmatory		X
		Abbott Prism HBsAg		X
		Viral load		X
		Anti-HBc IgM & Total		X
NAT Only Positive	NAT Confirmatory	NAT Confirmatory	X	
	Abbott Prism HBsAg	Abbott Prism HBsAg	X	
	Viral load	Viral load	X	
	Anti-HBc IgM & Total	Anti-HBc IgM & Total	X	
	Anti-HBs	Anti-HBs	X	
	Genotyping	Genotyping (if no index sample available)		X

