Finally, objective 2a will examine the relationship between the proportion of donors identified with incident HIV infection containing drug resistance mutations and the proportion of HIV-positive individuals receiving anti-retroviral therapy at a population-level in South Africa using available published data on the overall South Africa population. Given that we are able to identify sufficiently detailed population data, first, we will visually examine the relationship between the two types of proportions. Based on the visual examination and a sufficient amount of data, we will regress the proportion of donors identified with incident HIV infection containing drug resistance mutations on the proportion of HIV-positive individuals receiving anti-retroviral therapy at a population-level. Model diagnostics will determine whether or not

an appropriate model of the relationship has been determined. In addition, nonparametric modeling will be used to determine if a relationship exists.

The purpose of objective 2b is to determine HBV genotype profiles among HBV positive donors with recently acquired infection based on year of donation and site of collection, and correlate findings with donor demographics and risk behaviors derived in objective 2a. The outcome variable is HBV genotype. That is, a nominal categorical variable. The predictor variables believed to be associated with HBV genotype are year of donation and site of collection. Other variables, e.g., demographic variables and predictor variables identified in objective 2a, will be examined to understand their relationship to HBV genotype. The association between the outcome variable and predictor variable will be examined using categorical data analysis techniques. Bivariate analysis will be conducted using Chi-square tests. Analyses that include more than one predictor variable will be conducted using generalized logit models, which may include interaction terms. In addition, nonparametric modeling will be used when there are multiple predictor variables.

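### Section 4.9 specifies no comparison of incident with prevalent HBV genotypes, which is what hypothesis 2b is about

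*Protocol*

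**What the plan says.** Section 4 (Objectives) gives objective 2b two parts. The objective itself is descriptive: genotype profiles in donors with recent HBV, by donation year and collection site, related to demographics and risk behaviours. The single hypothesis beneath it is comparative: "Incident HBV infections will show differences in genotypes with genotype E increasing when compared to public health data on prevalent infections".

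Section 4.9 (Analytic Approach) then sets out the 2b analysis:

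- Population: "The purpose of objective 2b is to determine HBV genotype profiles among HBV positive donors with recently acquired infection".
- Outcome: "The outcome variable is HBV genotype", treated as nominal.
- Main predictors: "The predictor variables believed to be associated with HBV genotype are year of donation and site of collection".
- Further predictors: "Other variables, e.g., demographic variables and predictor variables identified in objective 2a, will be examined to understand their relationship to HBV genotype".
- Methods: chi-square tests for pairs of variables, generalized logit models for several predictors, and unspecified nonparametric modeling.

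For objective 2a, the hypothesis also needs outside data. There Section 4.9 has a separate paragraph that relates the proportion with resistance mutations to population treatment coverage, "using available published data on the overall South Africa population", first by visual inspection and then by regression if the data suffice.

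**The concern.** The hypothesis is a contrast between two kinds of infection, incident and prevalent, and the second kind is to come from outside the study. The 2b analysis set contains only the first kind. Infection type is constant in it, so no model fitted to it can estimate the contrast.

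At stake is whether the study can report on hypothesis 2b at all. Without a named comparator and a stated comparison, the report either says nothing on the hypothesis or uses a reference series chosen after the incident genotypes are known. The second route leaves room to pick a series that makes genotype E look raised.

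**Working it through.** The main check is textual. The protocol states no power, reference proportion or effect size for objective 2b, so there is no figure of its own to reproduce.

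**1. What each planned 2b test addresses**

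| Planned analysis (Section 4.9) | Null hypothesis | Bears on incident versus prevalent? |
|---|---|---|
| Genotype by year | Genotype mix is the same across years among incident cases | No |
| Genotype by site | Genotype mix is the same across sites among incident cases | No |
| Genotype by demographics and other predictors | Genotype is independent of these among incident cases | No |
| Generalized logit, nonparametric models | The same, for several predictors jointly | No |

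The year test could show genotype E rising among incident cases during enrollment. That is not a comparison with prevalent infection.

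**2. Whether another section supplies the comparator**

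- The synopsis plans "HBV genotype and viral load in all incident HBV infections (Objective 2"), and so covers incident infections only.
- Table 2 (Section 4.2.1) lists, for donations positive on both NAT and serology, "Genotyping if anti-HBc negative". Concordant prevalent infections are therefore not typed.
- Table 2 lists genotyping of NAT-only positives without an anti-HBc condition, so a few non-incident donors may be typed. They are not planned as a comparison group, and they are not the public health data that the hypothesis names.
- Section 4.5 describes the genotyping assay and no comparison data.

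No section names a source of prevalent HBV genotypes.

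**3. What a direct comparison could deliver (illustration)**

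Inputs: n1 = 150 incident cases, the enrollment target in Section 4.8.1. The published series size n0 and all genotype E frequencies are assumptions. The test is Fisher's exact test, two-sided at 0.05. Power is the sum, over all pairs of counts (a, b) with p ≤ 0.05, of Bin(a; 150, p1) × Bin(b; n0, p0).

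| Prevalent E (p0) | Incident E (p1) | n0 | Power |
|---|---|---|---|
| 2% | 4% | 300 | 22% |
| 3% | 5% | 300 | 16% |
| 5% | 8% | 300 | 22% |
| 2% | 8% | 300 | 81% |
| 2% | 8% | 100 | 47% |

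The approximate 95% interval for the difference shows why, from SE = √[p1(1−p1)/n1 + p0(1−p0)/n0]:

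- 4% against 2%: √(0.04×0.96/150 + 0.02×0.98/300) = √(0.000256 + 0.000065) = 0.0179. The difference is 2.0 points ± 3.5, which includes zero.
- 8% against 2%: √(0.08×0.92/150 + 0.000065) = √(0.000491 + 0.000065) = 0.0236. The difference is 6.0 points ± 4.6, which excludes zero.

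So the direct comparison can detect a large rise in genotype E but is imprecise for a modest one, and it depends on the size of the published series.

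**The case against.** The strongest reply is that the planned analysis does match the text of objective 2b, which asks for profiles by year and site. That stands. The year and site tests have a proper purpose, and the protocol nowhere presents them as the test of hypothesis 2b. A reader might infer that the protocol chose the wrong test, or would take a significant site result as support for the hypothesis. The documents do not support that reading; the defect is an omission.

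A second reply is that the comparison could be left to the statistical analysis plan, which is not at hand. The hypothesis already names the type of comparator, the study will produce the incident genotype E proportion, and setting it beside a published figure needs no model. This has some force for the exact test and the reference series. It does not remove the point, because Section 4.9 fixes a specific analysis for 2b and leaves out the one contrast that its hypothesis states, while writing out the external comparison for 2a.

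A third reply is that the word increasing may mean a time trend, which the year test covers. The hypothesis goes on to name prevalent infections as the comparator, so a trend among incident cases is at most part of it.

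It also stands that 2b is not among the objectives for which the study was powered, and that the genotypes remain available, so the comparison can be added without loss of data.

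**Conclusion.** The point holds as an omission: hypothesis 2b has no specified analysis, because every 2b analysis in Section 4.9 is made within incident cases and no prevalent comparator is named. This rests on the text alone and needs no assumption about genotype frequencies. It should be corrected, but it concerns molecular surveillance and does not touch the case-control objectives.

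It would go too far to say that the hypothesis can never be tested, since the data will exist and an analysis plan not seen here may supply the comparison. It would also go too far to quote a large power gap between the planned tests and a direct comparison as a measured loss. A test of one null rejects at about its alpha level when only an unrelated alternative is true; that follows by construction. Any other figure depends on assumed genotype frequencies and site patterns. The powers shown (16% to 81% with a series of 300, and 47% for 2% against 8% with a series of 100) only indicate what the missing comparison could achieve. They take 150 as the number typed. It could be higher, because index specimens are typed and Section 4.8.1 expects up to about 100 incident infections a year.

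**What to change.** In the 2b paragraph of Section 4.9:

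1. Name the published source of prevalent HBV genotypes before the incident genotypes are analysed, with its numerator and denominator for genotype E.
2. Estimate the genotype E proportion among incident cases with a 95% CI.
3. Compare it with the published numerator and denominator, by a difference in proportions with CI or Fisher's exact test, so that sampling error in the published figure is counted.
4. Keep the year and site tests, labelled as a description of variation within incident cases.
5. State as limitations that the published series may differ from donors in region, age and period, and that precision is low for modest rises in genotype E.

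If no suitable published series exists, restate hypothesis 2b as a description within incident cases. The same edit can reconcile a cross-reference: Section 4 links 2b to risk behaviours from Objective 1, Section 4.9 to those from objective 2a.

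The cost is a few sentences and a literature search, with no new participants or assays. The protocol cites no prevalent HBV genotype series, so whether a usable one exists has to be established first.
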